#### Screening Period: Week -1 (as needed)

Subjects taking no concomitant analgesic medication for their painful diabetic neuropathy at Visit 1 may directly begin Week -1 of the Screening Period. Serious adverse event reporting will begin at the time informed consent is obtained and will end 30 days after the last dose of study drug.

#### Baseline Visit: Week 0/Visit 2

At the Visit 2 (Baseline Visit), study personnel will verify eligibility with the inclusion and exclusion criteria when the subjects are on site and perform safety assessments prior to randomization.

The appropriate use of rescue medication will be assessed by inventory of the returned tablets, as well as by subject interview. Subjects will be asked a nonleading question to assess potential adverse events. Use of concomitant medications will be documented. Additional procedures during Visit 2 will include the S-STS, an ECG, and vital signs (blood pressure and pulse after sitting or lying supine for at least five (5) minutes). Blood (8 hour fast) samples will be collected for hematology, serum chemistry, and urine sample will be collected for urinalysis testing. Subjects will undergo drug screens using a local urine testing kit. Subjects who test positive for benzodiazepines inconsistent with protocol specified allowed prescriptions, psychoactive cannabinoids (e.g., marijuana, THC) inconsistent with subject reported use, PCP, opioids,

cocaine or amphetamines, will not be allowed to continue in the study. Female subjects of childbearing potential will be tested for pregnancy using a local urine testing kit and will be counseled to continue using highly effective contraception.

Pain scores reported by subjects during the Screening Period will be evaluated by the interactive response technology (IRT) system for raw score and for variability among scores after transmission of pain scores from the handheld devices to determine randomization eligibility.

Subjects whose mean of the daily average pain intensity score during the preceding seven (7) days within the protocol-defined algorithm and whose compliance with daily diary completion is found to be adequate will be eligible for randomization. The absolute pain scores and variability among scores, as well as the actual percentage required for diary compliance, will be masked to investigators and subjects. Subject eligibility for randomization into the study based on these variables will be communicated to the investigator via the IRT system. The IRT system will notify the site if the subject is "Eligible" or "Not eligible." No other information will be provided.

Eligible subjects will be randomized to receive either doses of oral NYX-2925 50 mg or placebo daily for 12 weeks. Investigators and subjects will be both blinded to treatment allocation and masked to the randomization criteria. Subjects will be dispensed a four-week supply of study drug and instructed to take one (1) capsule by mouth once daily. The first dose of study drug will be taken in the clinic during Visit 2 (Week 0). Subjects will be instructed to take study drug daily throughout the study. Acetaminophen will be dispensed/re-dispensed for use as rescue medication for DPN related pain; and instructions on not to exceed 2 g/day (one to two 500 mg tablets every 6 hours as needed up to 4 tablets total) will be reinforced.

Adverse events will be collected from the time of study drug administration through the last day of the subject's participation in the study.

Subjects will be instructed to continue entering their average pain intensity, worst pain intensity, average pain upon walking, and usage of rescue medication over the past 24 hours into their study-issued handheld device every night. Every morning upon awakening, subjects will complete the DSIS and confirm they have taken their study drug in the past 24 hours via their study-issued handheld device. Pain diary compliance will be reviewed by the study staff, and reporting instructions will be reinforced. Subjects will be reminded of appropriate expectations around their participation in a clinical study and the importance of consistently and accurately reporting their pain intensity throughout the study. Each subject will undergo educational training on Accurate Pain Reporting (APR®) and Placebo Response Reduction (PRR®) via an electronic learning management system, aLearn® [Analgesic Solutions, Wayland, MA].Review of these educational materials will be repeated for all subjects within the aLearn® platform at each site-based visit, with the exception of the final visit. An ongoing blinded data review (e.g., if pain score variability is increased on a subject or site level) will be conducted to monitor these metrics [Analgesic Solutions, Wayland, MA].

The following scales will be completed at the Baseline Visit (Visit 2): Brief Pain Inventory for Diabetic Peripheral Neuropathy (BPI-DPN), the Norfolk Quality of Life Questionnaire - Diabetic Neuropathy (QOL-DN), Patient Global Impression of Severity (PGI-S)Pain Catastrophizing Scale (PCS) and Sheehan – Suicidality Tracking Scale (S-STS).

The subject will be given a printed copy of the study specific S-STS to take home and complete during the Week 2/Visit 3 telephone or videoconference visit.

#### Treatment Period: Week 2/Visit 3

Subjects will be contacted by the clinic study staff via telephone or videoconference at the end of Week 2 (Visit 3) for assessment of compliance with study drug, rescue medication use and diary entries. The appropriate use of study drug and rescue medication will be assessed by subject interview. Subjects will be instructed to take one capsule of study drug by mouth once daily. Rescue medication, if required should not exceed 2g/day (one to two 500 mg tablets every 6 hours as needed up to 4 tablets total for DPN related pain.

Pain diary compliance will be reviewed by the study staff, and reporting instructions will be reinforced. Adverse events will again be assessed by asking the subjects a nonleading question. Misuse and abuse-related events will be assessed using the Misuse, Abuse, and Diversion Drug Event Reporting System® (MADDERS [Analgesic Solutions, Wayland, MA]). Use of concomitant medications will be documented.

The subject will be asked to complete the printed copy of the S-STS given to them at their Baseline Visit while communicating with the site staff. The staff will review the subject's answers to the S-STS and recommend corrections, only where the form has been completed incorrectly. The completed S- STS source document will be mailed back to the clinic or returned at the next study visit to be filed in the subject's chart and entered into the eCRF system. A subject may be asked to return to the clinic, per Investigator discretion, for additional study specific training or examination. Any unscheduled return to the clinic visit should be entered as an Unscheduled Visit in the eCRF and IRT systems.

Subjects will be instructed to continue entering their average pain intensity, worst pain intensity, average pain upon walking, and rescue medication use over the past 24 hours into their studyissued handheld device every night. Every morning upon awakening, subjects will complete the DSIS and confirm they have taken their study drug in the past 24 hours via their study-issued handheld device. Subjects will be reminded of appropriate expectations around their participation in a clinical study and the importance of consistently and accurately reporting their pain throughout the study.

Review of these educational materials will be repeated for all subjects within the aLearn® platform at each site-based visit, with the exception of the final visit. An ongoing blinded data review (e.g., if pain score variability is increased on a subject or site level) will be conducted to monitor these metrics [Analgesic Solutions, Wayland, MA].

The following scales to be completed at Week 2 (Visit 3) visit via telephone or videoconference: S-STS.

#### Treatment Period: Week 4/Visit 4

Subjects will return to the clinic at the end of Week 4 (Visit 4) for assessment of compliance with study drug and rescue medication use. The appropriate use of study drug and rescue medication will be assessed by inventory of the returned study drug and rescue medication, as well as by subject interview. Subjects will be dispensed a four-week supply of study drug.

Subjects will be instructed to take one capsule of study drug by mouth once daily. Rescue medication will be dispensed/re-dispensed to the subject with instructions not to exceed 2g/day (one to two 500 mg tablets every 6 hours as needed up to 4 tablets total) for DPN related pain.

Pain diary compliance will be reviewed by the study staff, and reporting instructions will be reinforced. Adverse events will be elicited by asking the subject a nonleading question. Misuse and abuse-related events will be assessed using MADDERS (Analgesic Solutions, Wayland, MA). Use of concomitant medications will be documented. Additional procedures during Visit 4 will include S-STS and vital signs (blood pressure and pulse after sitting or lying supine for at least five (5) minutes). Blood (8 hour fast) samples will be collected for hematology, serum chemistry, and urine sample will be collected for urinalysis testing. Subjects will undergo drug screens using a local urine testing kit. Subjects who test positive for benzodiazepines inconsistent with protocol specified allowed prescriptions, psychoactive cannabinoids (e.g., marijuana, THC) inconsistent with subject reported use, PCP, opioids, cocaine or amphetamines, will not be allowed to continue in the study. Female subjects will be tested for pregnancy using a local urine testing kit, if clinically indicated for females of childbearing potential. Female subjects of childbearing potential will be counseled to continue using highly effective contraception.

Subjects will be instructed to continue entering their average pain intensity, worst pain intensity, average pain upon walking, and rescue medication use over the past 24 hours into their studyissued handheld device every night and to complete the DSIS and confirm they have taken their study drug in the past 24 hours via their study-issued handheld device in morning. Subjects will be reminded of appropriate expectations around their participation in a clinical study and the importance of consistently and accurately reporting their pain throughout the study. Review of these educational materials will be repeated for all subjects within the aLearn portal at each site-based visit, with the exception of the final visit. An ongoing blinded data review (e.g., if pain score variability is increased on a subject or site level) will be conducted to monitor these metrics [Analgesic Solutions, Wayland, MA].

The following scales will be completed at Week 4 (Visit 4): BPI-DPN, Patient Global Impression of Change (PGI-C), QOL-DN and S-STS.

#### Treatment Period: Week 8/Visit 5

Subjects will return to the clinic at the end of Week 8 (Visit 5) for assessment of compliance with study drug and rescue medication use. The appropriate use of study drug and rescue medication will be assessed by inventory of the returned study drug and rescue medication, as well as by subject interview. Subjects will be dispensed a four-week supply of study drug.

Subjects will be instructed to take one capsule of study drug by mouth once daily. Rescue medication will be dispensed/re-dispensed to the subject with instructions not to exceed 2g/day (one to two 500 mg tablets every 6 hours as needed up to 4 tablets total) for DPN related pain.

Pain diary compliance will be reviewed by the study staff, and reporting instructions will be reinforced. Adverse events will be elicited by asking the subject a nonleading question. Misuse and abuse-related events will be assessed using MADDERS (Analgesic Solutions, Wayland, MA). Use of concomitant medications will be documented.

Additional procedures during Visit 5 will include S-STS and vital signs (blood pressure and pulse after sitting or lying supine for at least five (5) minutes). ECG would be conducted. Blood (8

hour fast)) samples will be collected for hematology, serum chemistry, and urine sample will be collected for urinalysis testing. Subjects will undergo drug screens using a local urine testing kit. Subjects who test positive for benzodiazepines inconsistent with protocol specified allowed prescriptions, psychoactive cannabinoids (e.g., marijuana, THC) inconsistent with subject reported use, PCP, opioids, cocaine or amphetamines, will not be allowed to continue in the study. Female subjects will be tested for pregnancy using a local urine testing kit, if clinically indicated for females of childbearing potential. Female subjects of childbearing potential will be counseled to continue using highly effective contraception.

Subjects will be instructed to continue entering their average pain intensity, worst pain intensity, average pain upon walking, and rescue medication use over the past 24 hours into their studyissued handheld device every night. Every morning upon awakening, subjects will complete the DSIS and confirm they have taken their study drug in the past 24 hours via their study-issued handheld device. Subjects will be reminded of appropriate expectations around their participation in a clinical study and the importance of consistently and accurately reporting their pain throughout the study. Review of these educational materials will be repeated for all subjects at each site-based visit, with the exception of the final visit. An ongoing blinded data review (e.g., if pain score variability is increased on a subject or site level) will be conducted to monitor these metrics [Analgesic Solutions, Wayland, MA].

The following scales will be completed at Week 8 (Visit 5): PGI-C and S-STS.

#### Treatment Period: Week 12/Visit 6 or Early Termination Visit

During Week 12 (Visit 6) or Early Termination Visit, subjects will return to the clinic for assessment of compliance with study drug and rescue medication use. The appropriate use of study drug and rescue medication will be assessed by inventory of the returned study drug and rescue medication, as well as by subject interview. Subjects will return the study-issued handheld device and other materials to the study site. Pain diary compliance will be reviewed by the study staff. Adverse events will be assessed by asking the subjects a nonleading question. Misuse and abuse-related events will be assessed using MADDERS (Analgesic Solutions, Wayland, MA).

Use of concomitant medications will be documented. Additional procedures during Visit 6/Early Termination Visit will include S-STS and vital signs (blood pressure and pulse after sitting or lying supine for at least five (5) minutes). Body weight will be measured, a brief physical examination performed, and ECG would be conducted. Blood (8 hour fast) samples will be collected for hematology, serum chemistry, HbA1c, and urine sample will be collected for urinalysis testing. Female subjects of childbearing potential will be tested for pregnancy using a local urine testing kit. Subjects will a undergo drug screens using a local urine testing kit.

The following scales will be completed at the Week 12 (Visit 6)/Early Termination Visit: BPI-DPN, PGI-C, QOL-DN, PCS and S-STS.

A safety follow-up telephone call will be made to the subject within 7-10 days and then approximately 30 days after week 12/final visit to assess for any AE/SAE closure and any newly reported SAEs.

The schedule of assessments is provided in Table 3.

# FINAL Version 8 25 June 2021

# Table 3Schedule of Procedures

Study Period	Screening	Baseline		Treatm	ent Period	
Study Week	1 to 4	Week 0	Week 2	Week 4	Week 8	Week 12/
(Day)	weeks a (-28 to -1)	(1±2) b	(14 ± 2)	(28 ± 4)	(56 ± 4)	ET b (84 ± 4)
Study Visit	Visit 1	Visit 2	Visit 3 w	Visit 4	Visit 5	Visit 6
Assessment						
Informed consent prior to any study procedure c	Х					
Assess inclusion/exclusion criteria	Х	X d				
APR®/PRR® training via aLearn®e	Х	Х	Х	Х	Х	
Education on appropriate expectations around participation in a clinical study e	Х	Х	X	Х	Х	
Michigan Neuropathy Screening Instrument (MNSI)	Х					
Masquerading Disorders Tool (MDT)	Х					
Demographic characteristics (age, sex, race, and ethnicity)	X					
Medical history	Х					
Height t	Х					
Body weight t,u	Х					Х
Vital signs (blood pressure and pulse after sitting or lying supine for at least 5 minutes) $^{f}$	Х	x		х	х	Х
Physical examination g	Х					Х
Triplicate electrocardiograms (3 separate ECGs) with a minimum of 2 mins gap between each ECG. V	Х					
Electrocardiogram (ECG) after at least 5 minutes in supine position		Х			X	X
Urine pregnancy test for females of childbearing potential h	Х	Х		Х	Х	Х
Urine Drug screens i	х	Х		Х	Х	Х
Obtain samples for hematology, chemistry, and urinalysis j	X j	Х		Х	Х	ť X
Discontinue all concomitant analgesic medications k	Х					
Dispense handheld electronic diary	X					
Clinical Protocol Amendment #7 Masked NYX-2925-2008

FINAL Version 8 25 June 2021

Study Period	Screening	Baseline		Treatn	nent Period	
Study Week	1 to 4	Week 0	Week 2	Week 4	Week 8	Week 12/
(Day)	weeks a (-28 to -1)	(1±2) b	(14 ± 2)	(28 ± 4)	(56 ± 4)	ET b (84 ± 4)
Study Visit	Visit 1	Visit 2	Visit 3 w	Visit 4	Visit 5	Visit 6
Return handheld electronic diary						X
Dispense/re-dispense rescue medication (acetaminophen) 	Х	Х		Х	Х	
Return rescue medication and perform accountability m		Х		Х	Х	X
Record average pain intensity, worst pain intensity, average pain upon walking and rescue medication use over past 24 hours at bedtime for each day n	X	X	X	X	Х	X
Record Daily Sleep Interference Scale (DSIS) each morning °	х	Х	Х	Х	Х	Х
Assess handheld diary compliance		X	X	X	Х	X
$\mathbf{r} = 1 = 1 = 1 = 1 = 1 = 1$						
Kandomize eligible subjects		X				
Dispense study drug		Х		Х	Х	
First dose of study drug (in the clinic)		Х				
Confirm daily study drug dosing in past 24 hours each morning p		Х	Х	Х	Х	Х
Return study drug and assess compliance m				Х	Х	Х
Pain Catastrophizing Scale (PCS)		Х				X
Brief Pain Inventory for Diabetic Peripheral Neuropathy (BPI- DPN)		Х		Х		Х
Norfolk Quality of Life Questionnaire – Diabetic Neuropathy (QOL-DN)		Х		Х		X
Patient Global Impression of Severity (PGI-S)	Х	Х				
Patient Global Impression of Change (PGI-C)				Х	Х	Х
Sheehan-Suicidality Tracking Scale (S-STS)	Х	Х	$\mathbf{X}^{w}$	Х	Х	Х
Misuse, Abuse, and Diversion Drug Event Reporting System ® (MADDERS) r			Х	Х	Х	Х
Concomitant medications	Хq	Х	Х	Х	Х	Х
Adverse events S	Х	Х	Х	Х	Х	Х
Safety follow-up calls						X x

Clin	ical Protocol Amendment #7 Masked NYX-2925-2008 25 June 202
a)	Subjects will discontinue all concomitant analgesic medications taken for pain related to diabetic peripheral neuropathy. Duration of the period will depend upon the analgesic(s) being discontinued, not to exceed 4 weeks. Subjects not taking any concomitant analgesic medications at Visit 1 may directly begin Week -1 of the Screening Period.
(q	ET=Early Termination. Subjects who prematurely discontinue randomized treatment will have Week 12 procedures performed. Diary completion ends the night before the Week 12 visit.
c)	Informed consent includes an additional consent for inclusion in a secure, proprietary, research subject database to screen for protocol violators. The main informed consent document may be executed up to 30 days prior to the screening visit. The date the first screening related activity is completed will be considered the subject's screening date. If the subject does not complete the screening visit within 30 days of signing the informed consent document the subject must be reconsented.
(p	Verify subject still meets all inclusion criteria and does not meet any exclusion criteria.
e)	Review of these educational materials via the aLearn portal will be repeated for all subjects at each site-based visit, with the exception of the final visit. Training at Visit 3 is per Investigator discretion. An ongoing blinded data review (e.g., if pain score variability is increased on a subject or site level) will be conducted to monitor these metrics [Analgesic Solutions, Wayland, MA].
f)	Vital signs will include blood pressure and pulse after sitting or lying supine for at least five (5) minutes, and prior to blood sample collection. Vital signs may be repeated up to three (3) times at screening, per the Investigator's discretion with a minimum interval of five (5) minutes between measurements. All vital signs should be recorded in the subject's source documents, with the final measurement of vital signs being entered into the eCRF system.
g)	A complete physical examination will be performed at Visit 1 and will include a comprehensive neurological examination. A brief physical examination will be performed at the Visit 6/Early Termination Visit.
(q	If clinically indicated for females of childbearing potential.
i.)	Urine drug screen kit for local testing.
Ĺ	Samples will be obtained following an 8 hour fast. Visit 1 tests will include HbA1c, triglycerides, HIV screening, hepatitis B screening, hepatitis C screening, CRP, and a thyroid panel (TSH, T3, T4 and free T4). Visit 6 (Week 12)/Early Termination Visit tests will include HbA1c. A CRP test will be conducted on each chemistry sample collected.
k)	Analgesic medications discontinued during the Screening Period cannot be restarted until after the Week 12 visit.
1)	Subjects will be instructed to take no more than 2 g/daily (one to two 500 mg tablets every 6 hours as needed up to 4 tablets total) for DPN related pain.
m)	Instruct study participants to bring all used and unused study drug and rescue medication to each visit for compliance monitoring.
(u	Numeric Rating Scale of pain intensity ( $0 = no$ pain to $10 = worst$ pain imaginable) will be completed once daily at bedtime. DSIS will be completed upon waking.
0	Starting after Visit 1.
(d	Starting after Visit 2, Subjects will be instructed to take one capsule of study drug by mouth once daily and confirm they have taken their study drug in past 24 hours via their study-issued handheld device upon awakening in morning.
(þ	Includes prior medications taken within the last 30 days.
r)	To be completed by Investigators or qualified Sub-investigators when potential abuse-related events are identified and upon completion of each subject's participation in the study.

- Adverse events will be collected from the time of study drug administration through the last day of the subject's participation in the study. Serious adverse event reporting will begin at the time informed consent is obtained and will end 30 days after the last dose of study drug. s)
  - BMI will be calculated based on height and body weight.
  - Weight to be obtained with a calibrated scale with appropriate range and resolution. Subject must remove shoes and bulky layers of clothes n t
    - Screening ECGs will be collected in triplicate (at least two (2) minutes apart). All other ECGs will be single ECGs.  $\widehat{}$
- where the form has been completed incorrectly. The completed S STS source document will be mailed back to the clinic or returned at the next study visit Visit Three (3) will be completed by telephone or videoconference. The subject will be asked to complete the printed copy of the S-STS given to them at their Baseline Visit while communicating with the site staff. The staff will review the subject's answers to the S-STS and recommend corrections, only to be filed in the subject's chart and entered into the eCRF system. (M
  - A safety follow-up call should be completed 7-10 days after Visit 6 completion. Final safety follow-up call to be made  $30 (\pm 5 \text{ days})$  days after Visit 6 completion. Investigator may ask subject to return for Unscheduled Visit, as needed. X)

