### 9.5. Serious Adverse Events

Serious adverse event reporting will begin at the time informed consent is obtained and will end 30 days after the last dose of study drug. Serious adverse events are reported to the Sponsor or designee using the provided form by email or fax to the following email address or fax number, respectively:

A serious adverse event is any adverse event occurring at any dose that results in any of the following outcomes:

- Death: "Death" is an outcome and is NOT the adverse event. In the event of death, the cause of death should be recorded as the adverse event. The only exception is "sudden death" when the cause is unknown.
- Is a life-threatening experience: Life-threatening adverse events include any adverse drug experience that, in the view of the Investigator, places the subject at immediate risk of

death from the reaction as it occurs. It does not include a reaction that, had it occurred in a more serious form, might have caused death.

- Requires inpatient hospitalization or prolongation of existing hospitalization.
- Results in a persistent or significant disability/incapacity: Disability is defined as a substantial disruption in a person's ability to conduct normal life functions.
- Results in a congenital anomaly/birth defect.
- Additionally, important medical events that may not result in death, be life-threatening, or require hospitalization may be considered a serious adverse event when, based upon appropriate medical judgment, they may jeopardize the subject and may require medical or surgical intervention to prevent 1 of the outcomes listed previously (e.g., allergic bronchospasm requiring intensive treatment in an emergency room or at home).

All serious adverse events that result in death or are life-threatening, regardless of causal relationship, must be reported to the Sponsor-designated Medical Monitor within 24 hours of the site's knowledge of the event. A copy of the initial serious adverse event report must be received within 1 business day.

All other serious adverse events or other events reportable to the United States Food and Drug Administration (FDA) and/or IRB will be forwarded to the Sponsor-designated Medical Monitor within 1 business day.

Any reported cases of COVID-19 that meet the SAE criteria above should be reported as per the protocol's defined SAE process.

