The serious adverse event report should provide as much of the required information as is available at the time. The following minimum information is required for reporting a serious adverse event: subject identification, reporting source, and an event outcome. Supplemental information may be transmitted using a follow-up report and should not delay the initial report. Aptinyx may contact the investigational site to solicit additional information or to follow-up on the event.

If there is any doubt whether the information constitutes a serious adverse event, the information will be treated as a serious adverse event for the purposes of this protocol. Serious adverse event reporting will begin at the time of consent and will end 30 days after the last dose.

All relevant documentation pertaining to a serious adverse event (e.g., additional diagnostic tests, consultation reports, discharge summaries, and postmortem reports) will be provided to the Sponsor-designated Medical Monitor in a timely manner. Serious adverse events will be followed until resolution or return to baseline (when worsening of a pre-existing condition is reported). If a serious adverse event does not return to baseline but reaches a stable situation that is not expected to change, this may be documented on the serious adverse event form.

The Sponsor may break the treatment code for subjects who experience a serious adverse event in order to determine if the individual case or group of cases requires expedited regulatory reporting. Individual treatment codes will be available to limited staff who are responsible to break codes for reporting purposes.

For each SAE, the Investigator and Sponsor will independently assess whether there is a reasonable possibility that the event may have been caused by the study drug ("drug-related"). The Sponsor will evaluate each drug-related SAE to determine if the event was unexpected. If the SAE is assessed to be both drug-related and unexpected, the Sponsor or designee will notify all

Investigators, and will report it to the appropriate regulatory authorities as required by applicable local regulations. The Sponsor or designee will report SAEs, including narratives, to the U.S. FDA and local regulatory authorities as required by 21 CFR 312.32 and the International Conference on Harmonisation (ICH) Guideline for Good Clinical Practice. The Investigator is responsible for notifying his/her respective IRB.

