#### 10.3.4. Week 12/Visit 6/Early Termination

At Week 12 (Visit 6) or at the time of early termination from the study, the following procedures and assessments will be performed/assessed:

- Concomitant medication use
- S-STS
- Adverse events
- MADDERS
- Body weight
- Vital signs (blood pressure and pulse after sitting or lying supine for at least five (5) minutes)
- Brief physical examination
- ECG after at least five (5) minutes in supine position
- Fasting (8 hours) blood samples for serum chemistry and hematology, including HbA1c
- Urine sample for urinalysis
- Urine pregnancy test for females of childbearing potential
- Urine drug screen
- BPI-DPN
- PGI-C
- QOL-DN
- PCS

- Compliance with entry into daily diary of pain intensity, rescue medication use, and study drug administration
- Rescue medication return and assessment of appropriate use by inventory of returned tablets, as well as by subject interview
- Study drug return and assessment of compliance by inventory of returned capsules, as well as by subject interview
- Study-issued handheld device and other equipment/documents return
- After completion of the study visits, the site will contact the subjects by telephone within 7-10 days to complete a safety follow-up call. The Investigator, at their discretion, may ask subject to return for an Unscheduled Visit for any safety concerns, abnormal laboratory or ECG findings.
- A final call will be made to the subject approximately 30 days after the final visit to assess for AE closure and any newly reported SAEs.

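### The final safety call may be made up to 5 days before the SAE reporting window closes, because Table 3 footnotes s and x do not line up (minor)

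*Protocol*

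**What the plan says.** Two protocol rules govern the end of safety follow-up, and both stand in the footnotes to Table 3.

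- **SAE window.** Footnote s states that SAE reporting "will end 30 days after the last dose of study drug". Section 9.5 says the same twice; the first statement is "Serious adverse event reporting will begin at the time informed consent is obtained and will end 30 days after the last dose". The anchor is the last dose, and no tolerance is given.
- **Follow-up calls.** Footnote x sets two calls. For the first: "A safety follow-up call should be completed 7-10 days after Visit 6 completion". For the second: "Final safety follow-up call to be made" at 30 days after Visit 6, with 5 days allowed either way. The anchor is Visit 6.

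Section 10.3.4 describes the second call ("A final call will be made to the subject approximately 30 days after the final visit") and gives its purpose, which is to close out AEs and pick up new SAEs. The Synopsis, Section 6.1 and SAP Section 1 also place it at about 30 days, without a numerical tolerance. Beyond these two calls, footnote x provides only for an Unscheduled Visit, which is optional.

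**The concern.** The final call is the only scheduled contact that could ask about SAEs at the end of the reporting window. Because the two rules have different anchors and only one has a tolerance, a site can follow footnote x exactly and make its last enquiry while footnote s still has days to run. An SAE in those days reaches the database only if the subject, or someone else, brings it to the site.

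At stake is the completeness of SAE ascertainment late in follow-up. Safety and tolerability stand under the primary objective (Section 5.1), and SAEs are a named safety endpoint (Section 5.3.3). The length of solicited follow-up would also vary between subjects according to when the call happened to be made.

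**Working it through.** The documents state no coverage figure to reproduce, so this is day arithmetic on their own rules.

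**Inputs**
- Call day *C*, in days after Visit 6: 30 − 5 = 25 to 30 + 5 = 35, which is 11 permitted days (Table 3, footnote x).
- End of SAE window: last dose + 30 days (Table 3, footnote s; Section 9.5).
- Lag *L*, the days by which the last dose precedes Visit 6. *L* cannot be negative, because study drug is returned at Visit 6 (Section 10.3.4). *L* = 0 is possible: the compliance intervals in SAP Section 6.2.9 add up to (Visit 6 date − first dose date) + 1 days, which counts the day of Visit 6 as a dosing day.

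**Formula**

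The SAE window ends at Visit 6 + (30 − *L*). The days left with no scheduled contact are

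gap = max(0, 30 − *L* − *C*).

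**Results (days)**

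| Last dose | Call Day 25 | 26 | 27 | 28 | 29 | 30–35 |
|---|---|---|---|---|---|---|
| Day of Visit 6 (*L* = 0) | 5 | 4 | 3 | 2 | 1 | 0 |
| 1 day before | 4 | 3 | 2 | 1 | 0 | 0 |
| 2 days before | 3 | 2 | 1 | 0 | 0 | 0 |
| 3 days before | 2 | 1 | 0 | 0 | 0 | 0 |
| 4 days before | 1 | 0 | 0 | 0 | 0 | 0 |
| 5 or more days before | 0 | 0 | 0 | 0 | 0 | 0 |

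- Maximum: 30 − 0 − 25 = 5 days, or 5/30 = 16.7% of the window. With *L* = 1: 30 − 1 − 25 = 4 days, or 4/30 = 13.3%.
- Permitted call days that leave a gap: 5 of 11 (45%) with *L* = 0, and 4 of 11 (36%) with *L* = 1.
- Average gap, on the assumption that calls spread evenly over the 11 days (the documents give no distribution): (5 + 4 + 3 + 2 + 1)/11 = 15/11 = 1.4 days (4.5% of 30) with *L* = 0, and (4 + 3 + 2 + 1)/11 = 10/11 = 0.9 days (3.0%) with *L* = 1.

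**A completer's last dose can fall earlier.** Bottles hold 32 capsules (Section 8.2). Visit 5 is at Day 56 ± 4 and Visit 6 at Day 84 ± 4 (Table 3), so the interval can reach 88 − 52 = 36 days. A bottle dispensed on Day 52 and used from Day 53 runs out on Day 84, which is 4 days before a Day 88 visit. The largest gap is then 30 − 4 − 25 = 1 day.

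**The case against.** The strongest reply is that footnote s and Section 9.5 define how long SAEs are *reported*, and nowhere promise a scheduled contact on or after the closing day. Subjects are told to report all adverse events (Section 9.4.3), sites must forward the SAEs they learn of (Section 9.5), and an Unscheduled Visit is available. A symmetric tolerance around a nominal day is also an ordinary design choice, and a call on the nominal Day 30 leaves no gap. All of this stands. It limits the point to solicitation, and it makes the 5-day figure a worst case. It does not remove the mismatch, because the call exists partly to pick up new SAEs and may be made before the period for them has ended.

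A reader might infer more than the documents support:

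- *That the 30-day SAE window is not delivered.* The reporting duty continues after an early call; only the active enquiry stops.
- *That the treatment comparison is biased.* The study is double-blind (Section 8.1), and the documents show no route by which call timing would differ by arm. Safety summaries are descriptive, without testing (Section 12.7).
- *That the absence of a DSMB analysis (SAP Section 8) makes it worse.* A DSMB would not find an event that nobody had reported.
- *That late SAEs would drop out of the serious-TEAE tables.* SAP Section 6.12.1 counts events through the last day of participation, but the documents do not define that day as the day of the final call, so this cannot be established.
- *That a delayed risk falls in these days.* The documents identify none. Section 4 describes plasma levels declining over 24 hours and minimal accumulation.

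**Conclusion.** The point holds, at minor severity. Table 3 allows a compliant final call up to 5 days before the stated SAE window closes, and nothing scheduled follows it. Five days needs both a call on the earliest permitted day and a last dose on the day of Visit 6. Under the even-spread assumption the average is about 1 day. Calls on Day 30 to 35 leave no gap, and neither does any call for a subject who stopped drug 5 or more days before the final or Early Termination visit.

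The maximum rests on one inference: that dosing can continue to the day of Visit 6. The SAP's compliance denominator supports this, but no passage states it as a rule. What is lost is active ascertainment over a few days for subjects called early. How many SAEs that would affect cannot be computed from the documents, but the number is likely to be small.

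**What to change.** Reconcile footnotes s and x so that the final call cannot fall before the stated SAE window ends. One way is to make the tolerance one-sided: 30 (+5) days after Visit 6. Since the last dose cannot follow Visit 6, last dose + 30 is never later than Visit 6 + 30, so every call in that window would come on or after the end of SAE reporting, even though the two anchors remain different. Carry matching wording into the Synopsis, Sections 6.1 and 10.3.4, and SAP Section 1.

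The cost is one footnote and the matching text. Some calls move later by up to 5 days, within the existing Day 35 limit, and no call or visit is added. The downside is that the permitted window shrinks from 11 days (25 to 35) to 6 (30 to 35), so a few more calls may fall out of window.
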